1.0 Research Design

1.1 Purpose/Specific Aims

The purpose of this study is to find an alternative, low risk option for managing muscle soreness in the older adult and elderly population.

A. Objectives

This study aims to compare how the topical application of essential oils *Eucalyptus globulus* and *Mentha x piperita* impact delayed onset muscle soreness after eccentric exercises compared to one another and to control.

B. Hypotheses / Research Question(s)

It is hypothesized that application of *Eucalyptus globulus* or *Mentha x piperita* oil will reduce perceived muscle soreness in subjects compared to control.

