1.3 Research Design and Methods

This study is designed as a randomized controlled interventional study with a rolling enrollment over the course of 6 months, with each individual subject's participation spanning over 72 hours. 20 subjects will be recruited for participation. 10 subjects will be included in the *Eucalyptus globulus* intervention group, and the remaining 10 will be placed in the *Mentha x piperita* group. A blocked randomisation list will be generated using an online randomizer in order to allocate subjects to each treatment group randomly. Each subject will have one upper extremity serving as the control, and one upper extremity which receives the intervention.

A. Research Procedures

Subjects

Subjects 50 years old and above with no previous resistance training sessions within the past year will be recruited at The Manor Health and Rehabilitation, a subacute rehabilitation and long-term care facility. A verbal explanation will be provided to the potential subjects by [name] or [name] on-site at the facility, including the fact that their care at the facility will not be affected by their decision to participate or not, and if they are interested in proceeding they will be asked to complete a survey regarding the subject's demographics (gender, age, hand dominance), ensure there are no hypersensitivities to the oils being used, upper extremity injuries within 1 year, and that they have the functional capacity for exercise of 3.5 metabolic equivalents or greater based on the Duke Activity Status Index. Subjects will be required to sign a consent to participate in screening. If participants pass the screening process they will again be informed of the study and all potential risks/benefits prior to signing an informed consent to partake in research.

Materials

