Subject outcomes will be based on a self-reported visual analog scale, which has previously been shown to have validity in subjectively quantifying perceived muscle soreness and used in prior studies. [14,16]. These outcomes will be recorded by investigators for both the intervention and control upper extremity at 24, 48, and 72 hours post-exercise.

C. Study Duration

Each subject will participate in this study for 72 hours. The overall study is anticipated to take place over a six month duration.

D. Endpoints

The primary endpoint will be a self-reported perceived muscle soreness using a visual analog scale. There are no secondary endpoints.

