1.5 Sample Size Justification

We anticipate a sample size of 20 subjects, 10 subjects in the *Eucalyptus globulus* group and 10 subjects in the *Mentha x piperita* group. This is based on previous studies which have investigated interventions for perceived muscle soreness and utilized a similar sample size for a power of 80% and a 1 tailed level of significance of p<0.05. [15]

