6.0 Data Management Plan

6.1 Data Analysis

Treatment analysis will involve a 1-way repeated measures ANOVA. Differences will be considered significant when p values are below an alpha level of 0.05.

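### With no primary time point, summary or contrast named, calling any difference with p<0.05 significant puts the chance of a false finding above 5%: about 10% to 31%, depending on which tests are run

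*Combined protocol and SAP*

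**What the plan says.** Section 6.1 is the whole analysis plan, in two sentences: "Treatment analysis will involve a 1-way repeated measures ANOVA", and "Differences will be considered significant when p values are below an alpha level of 0.05". It does not name the ANOVA factor, the contrasts that follow, an order of testing, a multiplicity adjustment or whether tests are one- or two-sided.

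Section 1.3 D states: "The primary endpoint will be a self-reported perceived muscle soreness using a visual analog scale. There are no secondary endpoints". Sections 1.3 B, 1.9 and 1.10 place that VAS at 24, 48 and 72 h after exercise; 1.3 B and 1.9 specify both arms.

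Section 1.1 A sets out to compare how the two oils "impact delayed onset muscle soreness after eccentric exercises compared to one another and to control". Section 1.1 B hypothesises a reduction with one oil or the other, so success with either would support it.

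The design in 1.3 is 10 subjects per oil, and "Each subject will have one upper extremity serving as the control, and one upper extremity which receives the intervention". Section 1.5 refers to "power of 80% and a 1 tailed level of significance of p<0.05".

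**The concern.** Three time points, two oils with their own control arms, and an oil-versus-oil question give up to nine differences. All belong to the one primary endpoint, since nothing is classed as secondary. A rule that calls each difference significant at 0.05 holds the error at 5% for each test, not for the study. A chance result for one oil at one time could be published as a positive finding.

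The named method does not settle the matter. A one-way within-subject ANOVA has no between-subject factor for oil, so oil versus oil needs a further test that the plan does not specify. If the ANOVA levels are the arm-by-time cells, F also responds to soreness rising and fading. Section 1.2 expects such a time course, with a peak within 24 to 48 h.

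**Working it through.** **Inputs from the documents.** Ten subjects per oil; one treated and one control arm each; three time points (1.3). Alpha 0.05 (6.1). One-tailed 0.05 and 80% power (1.5).

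**Inputs assumed.** The correlation between time points of the treated-minus-control difference is not given, so it is varied. The list of tests is not given either, so several families are shown. All rates are for no true oil effect.

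**The plan's own figures.** The sample size of 20 cannot be reproduced, because 1.5 gives no effect size or SD. Solving backwards with the noncentral t, 10 paired differences at 80% power detect 0.85 SD one-sided or 1.00 SD two-sided at 0.05. The stated alpha is right for one test: a single pre-named contrast rejects in 4.98-5.01% of simulated trials.

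**Independence formula.** 1 − 0.95^k gives:
- k = 2: 1 − 0.9025 = 9.75%
- k = 6: 1 − 0.7351 = 26.5%
- k = 9: 1 − 0.6302 = 37.0%. This is too high, because the oil-versus-oil contrasts reuse the same data.

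**Simulation.** At least 100,000 trials per setting. Oil versus control is a paired t-test per oil and time (six tests, 9 df). Oil versus oil is a two-sample t-test on the arm differences at each time (three tests, 18 df). False benefit means at least one oil-versus-control test that is significant in favour of the oil.

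| Between-time correlation | Six tests, two-sided 0.05 | Nine tests, two-sided 0.05 | False benefit, six two-sided tests | False benefit, six one-sided tests at 0.05 |
|---|---|---|---|---|
| 0 | 27% | 31% | 14% | 27% |
| 0.3 | 25-26% | 30% | 13% | 25% |
| 0.5 | 24% | 28% | 12-13% | 23% |
| 0.7 | 21% | 24-25% | 11% | 20% |
| 0.9 | 17% | 19% | 9% | 16% |

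The false-benefit column can be checked at correlation 0: 1 − 0.975^6 = 14.1%.

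**Narrower families.** One time-averaged two-sided test per oil gives about 9.7%. Adding a time-averaged oil-versus-oil test gives 11.5-12%.

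**Requiring a significant F first.** This run used one ANOVA per oil over the six arm-by-time cells, then that oil's three oil-versus-control tests.
- With an assumed decline of 1.5 SD from 24 to 72 h, F was significant in essentially every trial. The six tests still gave a false finding in 25.8%, 24.0%, 21.4% and 19.4% at correlation 0.3, 0.5, 0.7 and 0.8.
- With no change over time, the gated rate was 8.9%, 12.2%, 15.2% and 15.7%.

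**After the fix.** One time-averaged contrast per oil with Holm across the two oils gives 4.8-5.0%. The check is 1 − 0.975^2 = 4.9%.

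**The case against.** The strongest reply is that 6.1 lists no pairwise t-tests. Its second sentence can be read as setting alpha for the ANOVA, and the six or nine ungated tests are a construction. That is a fair limit on the size of the problem. A reader might infer that the plan carries a false-positive rate of 21-31%, but the documents support that only if each time point is tested separately and no F gate applies. Narrower readings give roughly 9-16%. The correlation is also unknown, and the rates fall as it rises. What remains is that no multi-test reading returns to 5%, and the objective cannot be met with one test.

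A reader might also infer that false efficacy claims would run at about five times the stated alpha. The documents do not support this for two-sided tests. About half of those errors favour the control arm, and oil-versus-oil tests say nothing about efficacy against control. Six two-sided tests give a false benefit in 11-14%. The 20-27% range needs one-sided tests at 0.05, which 1.5 suggests but 6.1 does not state.

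A third tempting reading is that the F test gives no protection at all. That holds only if the factor spans arm-by-time cells and soreness changes over time. Since 6.1 names no factor, the defensible statement is that protection is unreliable.

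Finally, each oil has its own subjects and control arms, so the oils could be treated as separate questions, and adjusting across them is a matter of judgement. The hypothesis, however, is supported by either oil, which favours adjusting. Treating the oils separately would still leave three time points per oil.

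**Conclusion.** The concern holds. The plan names no primary time point, summary or contrast and applies 0.05 to every difference, so the chance of at least one false significant difference exceeds 5%. It is about 10% with one time-averaged test per oil. With separate ungated tests at each time, it is 21-27% for six tests and 24-31% for nine at between-time correlation 0.7 to 0, and about 17% and 19% at 0.9. False claims that an oil reduces soreness run at 11-14% (six two-sided tests) or 20-27% (one-sided at 0.05) over the same range of 0.7 to 0. The defect is plain from the text. The exact size rests on the assumed correlation and on which tests would be run.

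**What to change.** In 1.3 D and 6.1:
- Name one primary contrast per oil: treated-arm minus control-arm VAS averaged over 24, 48 and 72 h, or at one named time.
- Test it as a paired contrast that replaces the one-way ANOVA as the primary test.
- Test the two oils with Holm at overall 0.05: the smaller p-value against 0.025 and, if that passes, the other against 0.05.
- State the sidedness, consistently with 1.5.
- Class the separate time points and oil versus oil as secondary, reported as estimates with 95% confidence intervals.

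This adds no subjects, visits or measurements. The price is the stricter first threshold: with 10 subjects and 80% power, two-sided, the detectable difference is about 1.14 SD of the paired difference instead of 1.00 SD. The sample-size statement in 1.5 must be updated to match. The change controls multiplicity only. It does not address bias from unmasked subjects (1.6) or from always treating the left arm (1.3).

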6.2 Data Security

Subject data will be stored in a secure file on a restricted drive that only investigators have access to. Subjects will be assigned a random identifier number. Names of subjects and their corresponding identifier number will be stored in one file, and a separate file will list the identifier number and the corresponding study data.

6.3 Data and Safety Monitoring

A. Data/Safety Monitoring Plan

Subject's pain level following exercise will be monitored throughout the 72 hour data collection period and if the intervention does not seem to provide adequate relief of muscle soreness (to a functional level) alternative options will be offered to relieve discomfort.

B. Data/Safety Monitoring Board Details

N/A

6.4 Reporting Results

A. Individual Subjects' Results

Results will not be disclosed to individual subjects.

B. Aggregate Results

Aggregate research results will be available to subjects upon request.

C. Professional Reporting

We plan to publish any findings in a scientific peer-reviewed journal and/or present the data at a research conference to share with the scientific community.

Protocol Title: Topical Eucalyptus globulus and Mentha x piperita on muscle soreness in older adults and the elderly Protocol Version Date: V3.03.20.21

D. Clinical Trials Registration, Results Reporting and Consent Posting

The investigation will be registered with Clinicaltrials.gov.

6.5 Secondary Use of the Data

N/A

7.0 Research Repositories - Specimens and/or Data

N/A

8.0 Approvals/Authorizations

Institutional Authorization Agreement has been obtained from CentraState Medical Center, which owns the Manor Health and Rehabilitation Center, for participation in research at this facility.

